1.3 Dose Rationale and Risk/Benefits

Local infiltration analgesia (LIA) involves injecting local anesthetic into the tissues around and within areas of the surgical wound, with the intent of providing satisfactory pain control, immediate mobilization of the surgical joint, and earlier discharge from the hospital.¹¹ Additional benefits for utilizing local infiltration analgesia techniques for the management of postoperative pain include its simplicity, decreased cost, reduced quadriceps weakness (in total knee arthroplasty patients), and reduction in risk of nerve injury following common peripheral nerve blocks.¹²

The use of interscalene brachial plexus nerve block remains the cornerstone for analgesia following shoulder surgery in comparison to suprascapular nerve block, intra-articular injection, and intravenous opioids.^{9,10} Local infiltration analgesia for shoulder surgery, despite showing to be less efficacious in terms of pain control, has not shown to be associated with adverse events.^{15,16} Theoretical advantages would include comparable pain scores to regional anesthesia techniques, while minimizing motor and/or sensory blockade as well as complications seen with interscalene brachial plexus blocks. Another advantage would be to avoid utilizing catheter based regional anesthesia techniques and its potential problems which include difficulty of catheter placement, catheter dislodgement, and leakage at insertion site. The theoretical advantages of local infiltration analgesia and the limited studies evaluating its use, particularly for total shoulder arthroplasty, are the basis for this study.

A complication associated with LIA would include local anesthetic systemic toxicity (LAST). Local anesthetic systemic toxicity is suspected if a patient has acute onset of central nervous system changes (tinnitus, metallic taste in mouth, perioral numbness) or cardiovascular changes (bradycardia, hypotension, EKG changes). This complication can occur with an intravascular injection, high systemic absorption depending on the vascularity of the site, and doses exceeding manufacturer's recommendation. LAST can also be seen with peripheral nerve blocks; therefore, the risk exists for all three intervention arms.

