By enrolling in this study there will be no additional risk in the operation or postoperative care as these are already established modalities of care, and all acceptable alternatives. Known risks for peripheral nerve blockade include the following: bleeding, infection, and nerve damage.

Since the benefits of local infiltration analgesia within a comprehensive multimodal analgesia clinical pathway have yet to be established for total shoulder arthroplasty, differences in the analgesia outcomes between these three intervention groups would provide for an evidence-based clinical pathway that will emerge as a result of this study.

2 Study Objectives

Primary Objective

We aim to test the hypothesis that patients undergoing total shoulder arthroplasty within a clinical pathway utilizing preemptive low-dose opioid and non-opioid medications for multimodal analgesia randomized to the continuous interscalene nerve block group will report a lower OBAS score on POD 1 (from 9 am to 12 pm) when compared to randomization to the single injection interscalene blockade and local infiltration analgesia groups.

Overall benefit of Analgesic Score (OBAS) is a recently validated tool measuring patient’s experience with their postoperative pain regimen.¹⁷ This simple 7 question (Q1 to Q7) scoring system entails a combination of pain intensity, adverse opioid events, and patient satisfaction. Per Lehmann et al, the total OBAS score is calculated via ‘sum items Q1 through Q6 and add [4 – score from Q7].’¹⁷ This score consists of a 29-point scale ranging from 0 (best) to 28 (worst); therefore, lower OBAS scores indicate more analgesic benefit. This will be administered to patients on POD 1 by the study team.

Secondary Objective

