3.4 Primary Safety Endpoints

These methods are already established procedures in the practice of perioperative pain control for a total shoulder arthroplasty. There is minimal risk of placing a peripheral nerve block. Those risks include infection, bleeding, and/or nerve damage. Patients will be monitored during the perioperative period for any adverse events (as defined below and in section 8). During regional anesthesia block placement, trained sedation nurses or anesthesia personnel (staff physicians, residents, or nurse anesthetists) will be monitoring patients. Patients will be monitored throughout the procedure utilizing the American Society of Anesthesiologists (ASA) standard monitors*, aspirating for blood or cerebral spinal fluid (CSF) prior to administration of local anesthetic solution in divided doses, frequent assessment of the patient's well-being via verbal communication, and having emergency medications and airway equipment readily available at all times. Performing this regional block is considered standard in our practice in order to provide optimal postoperative analgesia.

** blood pressure (non-invasive blood pressure cuff cycling every 3 to 5 minutes or continuous arterial blood pressure monitoring placed due to clinical judgment of covering anesthesiologist), 5 lead EKG, continuous pulse-oximetry, and continuous monitoring from operating room anesthesia personnel (if the procedure is performed in the operating room) or frequent assessments by nurses who are trained to care for patients receiving regional anesthesia blocks (if procedure is performed in block room)*

Patients undergoing local infiltration analgesia will have their block placed in the operating room by the surgeon under general anesthesia. Per ASA standards, trained anesthesia personnel will be directly monitoring the patient at all times during the surgical case, in addition to frequent

assessment of vital signs via standard monitors of care, which includes frequent blood pressure reading (blood pressure cuff or arterial line), rhythm analysis (5 lead EKG), heart rate (EKG), oxygen saturation (pulse-oximetry), temperature, and ventilation via end tidal carbon dioxide detection. Similar to regional block placement, blood pressure monitoring involves the following: non-invasive blood pressure cuff cycling every 3 to 5 minutes or continuous arterial blood pressure monitoring (placed due to clinical judgment of covering anesthesiologist).

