Patients admitted to the regular nursing floors will have a continuous pulse-oximeter if a continuous peripheral nerve block is present. In addition, vital signs (heart rate, oxygen saturation, and blood pressure) will be captured every 4 hours or more frequently if the clinical situation dictates in all postoperative orthopedic patients.

Daily follow-up will occur by the inpatient pain service and surgical team. Adverse events and/or complications will be monitored, which includes but not limited to, local anesthetic systemic toxicity, neurologic complications, hematoma, bleeding, infection, and wound problems. Nerve damage and assessment is part of the follow-up regarding this study and will be followed closely. In the event an infection was to occur, the PI would be notified, protocol would be followed, and investigators of the study would review the incident.

The principal investigator or a designated co-investigator of the study will be notified if a patient in the study requires an unanticipated ICU admission.

Please refer to section 8 for detailed explanation for management of adverse events or complications.

4 Subject Selection Enrollment and Withdrawal

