8.1 Definitions

Unanticipated Problems Involving Risk to Subjects or Others (UPIRTSO)

Any unanticipated problem or adverse event that meets the following three criteria:

- Serious: Serious problems or events that results in significant harm, (which may be physical, psychological, financial, social, economic, or legal) or increased risk for the subject or others (including individuals who are not research subjects). These include: (1) death; (2) life threatening adverse experience; (3) hospitalization - inpatient, new, or prolonged; (4) disability/incapacity - persistent or significant; (5) birth defect/anomaly; (6) breach of confidentiality and (7) other problems, events, or new information (i.e. publications, DSMB reports, interim findings, product labeling change) that in the opinion of the local investigator may adversely affect the rights, safety, or welfare of the subjects or others, or substantially compromise the research data, **AND**
- Unanticipated: (i.e. unexpected) problems or events are those that are not already described as potential risks in the protocol, consent document, not listed in the Investigator's Brochure, or not part of an underlying disease. A problem or event is "unanticipated" when it was unforeseeable at the time of its occurrence. A problem or event is "unanticipated" when it occurs at an increased frequency or at an increased severity than expected, **AND**
- Related: A problem or event is "related" if it is possibly related to the research procedures.

Non-UPIRTSO

A reportable event that does not meet the Mayo Clinic IRB's definition of a UPIRTSO.

Adverse Event

An untoward or undesirable experience associated with the use of a medical product (i.e. drug, device, biologic) in a patient or research subject.

Serious Adverse Event

Adverse events are classified as serious or non-serious. Serious problems/events can be well defined and include;

- death
- life threatening adverse experience
- hospitalization
- inpatient, new, or prolonged; disability/incapacity
- persistent or significant birth defect/anomaly

And/or per protocol may be problems/events that in the opinion of the sponsor-investigator may have adversely affected the rights, safety, or welfare of the subjects or others, or substantially compromised the research data.

All adverse events that do not meet any of the criteria for serious, should be regarded as **non-serious adverse events**.

Adverse Event Reporting Period

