8.5 Stopping Rules

Adverse events and serious adverse events, as defined in Section 8.1 of IND protocol, will be monitored by the study team for patient safety. Known serious adverse events associated with interscalene nerve blocks (SISB and CISB groups) include inadvertent intravascular injection⁺, local anesthetic systemic toxicity (LAST)*, inadvertent epidural or subarachnoid injection, and pneumothorax. Additionally, patients will be monitored throughout the procedure utilizing standard ASA monitors, aspirating for heme or cerebral spinal fluid (CSF) prior to administration of local anesthetic solution in divided doses, frequent assessment of the patient's well-being via verbal communication, and having emergency medications and airway equipment readily available at all times. Performing this regional block is considered standard in our practice and these methods are already established procedures in the practice of perioperative pain control for a total shoulder arthroplasty.^{4,5}

Serious adverse event associated with local infiltration analgesia (LIA group) is local anesthetic systemic toxicity (LAST).

⁺ *Inadvertent intravascular injection is suspected if a patient experiences sudden loss of consciousness, apnea, convulsions, hypotension, respiratory depression, or stroke symptomology.*

^{*} *Local anesthetic systemic toxicity is suspected if a patient has acute onset of central nervous system changes (tinnitus, metallic taste in mouth, perioral numbness) or cardiovascular changes (bradycardia, hypotension, EKG changes).*

LAST is a known serious adverse event with any local anesthetic administration. Preventive measures include high degree of suspicion, vital sign monitoring (blood pressure, EKG, oxygen saturation), using an appropriate dose of local anesthetic, injecting local anesthetic in divided dose, aspirating prior to injection of medication looking for heme, consider using epinephrine in solution as a vascular marker, being prepared to treat a LAST event immediately (checklist, external defibrillator, resuscitate medications, emergency airway equipment), and having lipid emulsion therapy readily available (standard of care).⁴⁶ We acknowledge that despite the rarity of these serious adverse events, the potential still exists.

Study stopping criteria includes:

CISB and SISB groups:

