- a) The study will stop if 5% of subjects in either group experience inadvertent intravascular injection, inadvertent epidural or subarachnoid injection, and pneumothorax.
- b) The study will stop if 5% of subjects in either group experience LAST.

LIA group

- a) The study will stop if 5% of subjects experience LAST.

We acknowledge that unanticipated adverse events may arise during this study.

CISB, SISB, and LIA groups:

- a) The study will stop if 5% of subjects in any group (4 patients) experience an unanticipated serious adverse event (as defined in section 8.1 of IND protocol).

If the study is stopped for any of the reasons listed above, a root cause analysis will be performed to determine cause of adverse event and relationship to study protocol. The study team will formulate an appropriate plan of action to ensure patient safety. Such a plan may include, but is not limited to, protocol modifications, immediate termination of accrual, and adjustments in management of previously enrolled participants continuing to undergo study interventions.

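### No stopping rule in section 8.5 names nerve damage, infection or bleeding, and the catch-all rule reaches them only through an expectation clause with no stated reference rate

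*Combined protocol and SAP*

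**What the plan says.** Section 1.3 states: "Known risks for peripheral nerve blockade include the following: bleeding, infection, and nerve damage". Section 3.4 repeats the same three for the block: "Those risks include infection, bleeding, and/or nerve damage". It adds: "Nerve damage and assessment is part of the follow-up regarding this study and will be followed closely".

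The text introducing the stopping rules in section 8.5 has a different list. It begins "Known serious adverse events associated with interscalene nerve blocks (SISB and CISB groups) include inadvertent intravascular injection" and continues with LAST, epidural or subarachnoid injection, and pneumothorax. The rules follow that list:

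- CISB and SISB, rule a: "The study will stop if 5% of subjects in either group experience inadvertent intravascular injection, inadvertent epidural or subarachnoid injection, and pneumothorax".
- CISB and SISB, rule b: 5% of either group with LAST.
- LIA: 5% with LAST.
- All groups: 5% of any group, glossed as 4 patients, who "experience an unanticipated serious adverse event (as defined in section 8.1 of IND protocol".

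Section 8.1 says that unanticipated "problems or events are those that are not already described as potential risks in the protocol" (it also refers to the consent document and the Investigator's Brochure). It then adds a second limb: an event is also unanticipated when it occurs more often or more severely than expected.

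**The concern.** Section 8.5 has two routes to a stop: a named list and a catch-all for the unforeseen. A serious nerve injury, infection or bleed after a block is on no list. Because the protocol describes it as a risk, the first limb of the 8.1 definition also keeps it out of the catch-all. The second limb could bring it back, but only by comparison with an expectation that the protocol does not state.

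Nerve injury is a harm that the protocol undertakes to follow, with a neurologic check at 12-16 weeks. As written, a cluster of serious cases in one arm would meet no rule with a stated threshold. Whether the trial paused would rest on judgement within the study team, in an unblinded trial for which the protocol sets up no independent monitoring board.

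**Working it through.** **The plan's own figure.** 0.05 × 43 = 2.15, so the first whole count at or above 5% of a planned group is 3 (3/43 = 7.0%). Four patients are 4/43 = 9.3% of a group; 4 is exactly 5% of 80. The gloss of 4 patients therefore does not follow from 43 per group. That is a separate point for the sponsor to settle, so both counts are carried below.

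**Events set against rules.**

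| Event | Described as a known risk or event | Named trigger in 8.5 |
|---|---|---|
| Intravascular injection | 8.5 | CISB, SISB |
| Epidural or subarachnoid injection | 8.5 | CISB, SISB |
| Pneumothorax | 8.5 | CISB, SISB |
| LAST | 1.3, 8.5 | all three groups |
| Nerve damage | 1.3, 3.4 | none |
| Infection | 1.3, 3.4 | none |
| Bleeding | 1.3, 3.4 | none |

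Being known is thus no reason for leaving an event off the list: every named trigger is itself a known event.

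**The catch-all.** I read the reference to section 8.1 as section 8.1 of this document. Persistent or significant disability is serious there, so a lasting disabling nerve injury qualifies as serious. On the first limb it is not unanticipated. On the second limb it is, if it exceeds expectation, but no expected frequency or severity for nerve damage, infection or bleeding appears in the protocol.

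**Chance of reaching a count if the events are named.** For one arm, P(X ≥ r) with X ~ Binomial(43, p). For any of three arms, 1 − (1 − P)³, taking the same rate in each arm and independence. The rates are assumptions; the protocol gives none. The count is taken over the full planned arm of 43.

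| Assumed rate p | r = 3, one arm | r = 3, any of three | r = 4, one arm | r = 4, any of three |
|---|---|---|---|---|
| 1% | 0.009 | 0.03 | 0.001 | 0.003 |
| 2% | 0.055 | 0.16 | 0.011 | 0.03 |
| 5% | 0.365 | 0.74 | 0.167 | 0.42 |
| 10% | 0.818 | – | 0.635 | – |

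**When late findings could act.** Assume that the 18 months include the last patient's 12-16 week contact and that accrual is even. Twelve weeks are 2.8 months and 16 weeks are 3.7 months, so accrual lasts 18 − 2.8 = 15.2 or 18 − 3.7 = 14.3 months. The lag from surgery to check is then worth 129 × 2.8/15.2 = 24 to 129 × 3.7/14.3 = 33 enrolments. A third event at rate p is expected after 3/p checks in that arm, or 3 × 3/p overall:

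- p = 20%: 15 checks in the arm, 45 overall, 69-78 enrolled, 51-60 still to enrol.
- p = 10%: 30 in the arm, 90 overall, 114-123 enrolled, 6-15 still to enrol.
- p = 5%: 60 in the arm, which exceeds 43, so a third event is not expected.

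Events seen in hospital would be counted sooner.

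**The case against.** Several counterarguments have weight.

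- **Other known risks are named.** A reader of 1.3 might infer that bleeding, infection and nerve damage are the only known block risks. They are not. Section 8.5 names four other known serious events, and 1.3 itself says of LAST: "LAST can also be seen with peripheral nerve blocks; therefore, the risk exists for all three intervention arms". The point is only that these three are absent from the stopping lists.
- **Known events are not shut out altogether.** A reader might infer that any number of nerve injuries among 43 patients would trigger nothing. The second limb of 8.1 contradicts that: a serious excess over expectation does reach the catch-all. The adverse event worksheet in 8.3.1 records whether an event was expected, so the clause can be used by judgement. The consent form, to which 8.1 also refers, was not available for this review and might give an expectation. What remains is that the protocol supplies no reference rate.
- **LIA is arguable.** Sections 1.3 and 3.4 tie the three risks to nerve blocks, and for LIA 8.5 associates only LAST. Nerve injury from infiltration may therefore already be unanticipated. The monitoring list in 3.4 covers all patients, however, so the reading is unsettled. If it holds, the same injury would count in LIA but not in the block groups.
- **Oversight exists.** Section 3.4 provides daily follow-up and review of any infection, section 8.6 provides regular assessment of serious adverse events, and the 8.5 criteria are introduced as a non-exhaustive list. None of this carries a threshold.
- **Time to act is limited.** One might subtract 24-33 from 129 and say that 96-105 patients are still to be protected. That counts from the first returned check, when no per-arm rule could yet fire. At an assumed 10% rate, few patients would remain when late findings reached three.

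**Conclusion.** The point stands in a limited form. Three risks that the protocol attributes to the blocks are in no named-event rule, and the catch-all applies to them only through a comparison for which the protocol gives no reference value. Sections 1.3, 3.4, 8.1 and 8.5 need to be reconciled. This is an inexpensive improvement to safety monitoring and does not affect the primary analysis.

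The benefit depends on how common the events are. At an assumed 10% rate in an arm, a count of 3 would be reached with probability 0.82 and a count of 4 with probability 0.64. For deficits found only at 12-16 weeks, the threshold would often be met after most patients are enrolled; the gain is larger for events seen in hospital. These figures rest on assumed rates, full arms of 43 and even accrual.

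**What to change.** In section 8.5, add for all three groups: nerve injury of the surgical extremity, infection, and bleeding or hematoma, where the event meets the 8.1 definition of serious and is at least possibly related to the block or infiltration on the WHO-UMC scale that the protocol already uses. Count these whether or not they are unanticipated, under the same per-group threshold that the sponsor settles for the other events.

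State that qualifying neurologic findings from the 12-16 week contact enter the running per-arm tally as each contact is completed. This should be explicit, because 8.1 sets a 7-week follow-up period for adverse event reporting while 8.2 collects events at 12-16 weeks.

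Both limits, seriousness and relatedness, are needed. Counting any persistent numbness or weakness could raise the background rate to a level where a chance stop is likely: at an assumed 5%, about 0.74 that at least one of three arms reaches 3 events, against about 0.03 at 1%. Without the relatedness condition, complications of the surgery itself could stop the trial.

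The cost is one added item in 8.5 and a tally of data already scheduled for collection. If the threshold is met, the result is the root cause analysis that 8.5 already provides. Stating expected rates in the protocol would instead make the 8.1 clause usable, but it would leave the three events off the named lists.

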8.6 Medical Monitoring

It is the responsibility of the Principal Investigator to oversee the safety of the study at his/her site. This safety monitoring will include careful assessment and appropriate reporting of adverse events as noted above, as well as the construction and implementation of a site data and safety-monitoring plan (see section 10 “Study Monitoring, Auditing, and Inspecting”). Medical monitoring will include a regular assessment of the number and type of serious adverse events.

9 Data Handling and Record Keeping

9.1 Confidentiality

Information about study subjects will be kept confidential and managed according to the requirements of the Health Insurance Portability and Accountability Act of 1996 (HIPAA). Those regulations require a signed subject authorization informing the subject of the following:

- What protected health information (PHI) will be collected from subjects in this study
- Who will have access to that information and why
- Who will use or disclose that information
- The rights of a research subject to revoke their authorization for use of their PHI.

In the event that a subject revokes authorization to collect or use PHI, the investigator, by regulation, retains the ability to use all information collected prior to the revocation of subject authorization. For subjects that have revoked authorization to collect or use PHI, attempts should be made to obtain permission to collect at least vital status (long term survival status that the subject is alive) at the end of their scheduled study period.

